- Known or suspected allergy to Dapagliflozin, excipients, or related products
- Pregnant, breast-feeding or the intention of becoming pregnant
- Females of childbearing potential who are not using adequate contraceptive methods

Withdrawal Criteria

Study subject may withdraw at will at any time.

Repeated eGFR <60 mL/min/1.73 m² and hypoglycaemic (< 70 mg/dl) episodes will mandate discontinuation of the patient from the study.

VISIT PROCEDURES

Once patient eligibility and written consent are obtained, the participant is then scheduled for the baseline (t0) clinic visit through the University of Miami UChart (Epic) electronic system. The visits will be coordinated by the research coordinator. Each patient will undergo a baseline echocardiographic study for the measurement of EAT and LVM. Each patient will also have a full physical examination, body weight, height, waist and hip circumference measured, a point of care of fasting glucose and haemoglobinA1c (HbA1c). Echocardiographic study will be performed on site by [name] and by an experienced cardiac imaging technician who will be trained to measure echocardiographic EAT by [name]. The same visit procedures will be repeated after 3 (t3) and 6 (t6) months.

DESCRIPTION OF STUDY SITE

UM Miller School of Medicine has been the site of several National Institutes of Health studies and many peer-reviewed, epidemiologic and health services research publication. The Division of EDM is fully equipped and trained to visit, follow up and manage patients with diabetes. UMMG-DRI is fully accredited and equipped to perform state-of-the-art diagnostic tests assisting in the diagnosis and management of diabetes. The Division is also equipped with a state-of-the-art echocardiographic unit, Siemens, Acuson, USA, for the measurement of the EAT. [name] pioneered the echocardiographic measurement of the epicardial fat and he is considered the leading expert in epicardial fat research

METHODOLOGY

Informed consent will be in place before any study related procedures will be conducted.

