Reliability of echocardiographic measurement of EAT will be assessed by the intra-class correlation coefficient. Inter- and intra-observer reproducibility will be evaluated by the intra-class correlation coefficient in all subjects. Echocardiograms will be read by [name] and an experienced cardiac imaging technician who will be blinded to the patients' study group. Previously published studies have shown that intra- and inter-observer reproducibility of epicardial fat measurement was excellent. Intra-class correlation coefficients varied from 0.90 to 0.98 and from 0.93 to 0.98, respectively indicating good reproducibility and reliability. Both readers will be blinded to the subjects' clinical data. Although its advantages overcome the disadvantages, echocardiography measurement may have some limitations. Echocardiographic EAT is a linear measurement at a single location and therefore may not reflect the variability of fat thickness or total epicardial fat volume

Echocardiographic LVM and LVH measurement

LV mass will be estimated by using the anatomically validated formula of Devereux, and then adjusted as LV mass/body surface area (BSA) and LV mass/height^{2.7} (h^{2.7}). Left ventricular hypertrophy (LVH) will be defined as LV mass/BSA >134 g/m² for men and >110 g/m² for women and as LV mass/h^{2.7} >51 g/m^{2.7} in both sexes. Relative wall thickness (RWT) will be calculated as 2 posterior wall (PW)/LV end – diastolic – diameter. Four LV geometric patterns (normal, concentric remodeling, concentric hypertrophy, and eccentric hypertrophy) will be determined using values of RWT and LV mass as follows: normal (no LVH and RWT < 0.44), concentric remodeling (no LVH and RWT > 0.44), concentric hypertrophy (LVH and RWT > 0.44), and eccentric hypertrophy (LVH and RWT < 0.44).

Physical Examination

All anthropometric measures will be obtained by the study nurse. Height (in cm) and weight (in kg) will be measured, and BMI will be automatically calculated as weight in kilograms divided by the square of height in meters (kg/m²). Waist circumference (in cm) will be measured as the minimum circumference between the lower rib margin and the iliac crest. Hip circumference (in cm) will be measured as the widest diameter over the greater trochanters). Blood pressure will be measured in the seated position, using an automated cuff and digital readout, and entered by the study nurse into the electronic database.

Blood Measurements

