Dapagliflozin reduces LVM through an effect on EAT. Based on our previous data (36) we know that LVM reduction is independently related to epicardial fat reduction. We hypothesize that LVM will reduce in the F-group and better than in the M-group. ANOVA test with 95% CI will be used to calculate the changes (Δ) in study parameters between baseline, 3 and 6 months in both F and M-group. Relations between Δ epicardial fat, Δ BMI, Δ waist circumference and Δ LVM will be calculated using simple linear regression analysis. Variables with a $p < 0.1$ value on univariate analysis will be entered in different multivariate analysis models to assess the independent determinants of Δ LVM, as dependent variables. Echocardiographic epicardial fat will be compared to BMI, waist circumference and to waist-hip ratio as independent predictor of Δ LVM. The optimum sensitivity and specificity of threshold values of EAT to predict reduction in LVM will be examined by receiver operating characteristics (ROC) analysis by plotting sensitivity vs. 100 – specificity.

DATA HANDLING AND RECORD KEEPING:

Data Collection: Each of the dedicated clinic exam rooms at the UMMG-DRI provides direct access to the clinical research study electronic data capture (EDC) eVelos system provided by the Clinical Research Informatics and Data Management Unit of the Center for Health Informatics and Bioinformatics at UM. The sponsor investigator and research coordinator will collect and manage the data.

ETHICS:

Informed Consent

Eligible and willing participant will be contacted by the research coordinator and consented. Previous to the signing of the informed consent, extensive oral and written information will be given to the subjects, including information about risks associated with Dapagliflozin treatment (in accordance with the updated Prescribing Information) before initiating any study related activity.

Confidentiality of data The sponsor investigator will explain that participant confidentiality will be maintained, data will only be identified by a number and that their consent forms with identification number will be kept locked in a filing cabinet.

Protections against Risk

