CONCOMITANT ILLNESSES AND MEDICATIONS:

Details of all concomitant illnesses and medication will be recorded at the first visit. Any changes in concomitant medication will be recorded at each visit. If the change influences the subject's eligibility to continue in the trial, the Sponsor will be informed. The information collected for each concomitant medication includes, at a minimum, start date, stop date or continuing, and indication. For each concomitant illness, date of onset, date of resolution or continuing, at a minimum, will be recorded.

SAFETY

Adverse Event (AE):

An AE is any undesirable medical event occurring to a subject in a clinical trial, whether or not related to the trial product(s). This includes events reported from the first trial related activity after the subject has signed the informed consent and until post treatment follow-up period as defined in the protocol. The following should not be recorded as AEs, if recorded as medical history/concomitant illness on the CRF at screening:

- Pre-planned procedure, unless the condition for which the procedure was planned has worsened from the first trial related activity after the subject has signed the informed consent
- Pre-existing conditions found as a result of screening procedures

Adverse events:

In the case of an AE, the sponsor-investigator will comply with all local legal, regulatory, and IRB requirements. The sponsor-investigator will be responsible for reporting of all adverse events including serious adverse events (SAE), suspected unexpected serious adverse reactions (SUSARs), serious adverse drug reactions (SADRs) to the competent authority and independent ethics committee/institutional review boards based upon federal regulations and local/IRB policies. The sponsor-investigator will report to Astra-Zeneca all SAEs, SUSARs, and SADRs at the same time such events are reported to regulatory authorities or within 15 days from the sponsor-investigator becoming aware of such adverse events, whichever comes first.

The sponsor-investigator will use the approved Updated Prescribing Information for Farxiga

The sponsor-investigator will collect the following information at minimum for each of these events:

1. Study name
2. Patient identification
3. Event (preferably a diagnosis)
4. Drug
5. Reporter identification

Clinical Laboratory Adverse Event:

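### EAT change is called an independent determinant of LVM change after comparison with other fat measures only; blood pressure, measured at every visit, should be in the model

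*Combined protocol and SAP*

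**What the plan says.** Study Hypothesis 2 (Statistical Considerations) is worded causally: "Dapagliflozin reduces LVM through an effect on EAT". The analysis behind it has three steps.

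- Screening: "Relations between Δ epicardial fat, Δ BMI, Δ waist circumference and Δ LVM will be calculated using simple linear regression analysis".
- Selection: "Variables with a $p < 0.1$ value on univariate analysis will be entered in different multivariate analysis models", in order to identify independent determinants of LVM change.
- Comparison of markers: "Echocardiographic epicardial fat will be compared to BMI, waist circumference and to waist-hip ratio as independent predictor of" LVM change.

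Blood pressure and treatment arm appear in none of these steps.

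The data nevertheless exist. Under Physical Examination, "Blood pressure will be measured in the seated position, using an automated cuff and digital readout, and entered by the study nurse" in the electronic database. Visit Procedures gives the baseline content, "Each patient will also have a full physical examination", and then states "The same visit procedures will be repeated after 3 (t3) and 6 (t6) months". Blood pressure is not named in the visit list itself. It sits under the Physical Examination heading, so a change from baseline should be available at both follow-up visits. Under Concomitant Illnesses and Medications, "Any changes in concomitant medication will be recorded at each visit", with the indication, so changes in blood-pressure drugs can be identified.

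**The concern.** Blood pressure is the load the left ventricle works against, so it is an obvious rival explanation for a change in LVM. The Background says that weight loss on this drug may come from fat loss, from fluid loss through osmotic diuresis, or from both, which leaves a haemodynamic route open. A model that adjusts EAT only for BMI and waist cannot separate that route from EAT. In such a model, independent means no more than independent of other fat measures.

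What is at stake is the mechanistic part of the secondary objective, that LVM falls by way of EAT. If patients whose EAT falls more also have larger falls in blood pressure, EAT change will predict LVM change even if epicardial fat does nothing to the ventricle.

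**Working it through.** **The plan's own figure.** None is given for LVM or for these regressions. The only power figure, 80% for a 1.2 mm EAT change, reproduces as a before-after calculation in one arm: 1.2/(3/√50) = 2.83; 2.83 − 1.96 = 0.87; Φ(0.87) ≈ 0.81. It does not enter what follows.

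**Inputs.** From the documents: 100 patients, attrition below 10% (hence n = 90 as the low end), two-sided α = 0.05. Assumed, because the documents give nothing: correlation of EAT change with blood pressure change (a) 0.2-0.4, correlation of blood pressure change with LVM change (b) 0.3-0.4, and a true EAT effect on LVM of zero.

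**Step 1: EAT alone.** The spurious EAT-LVM correlation is r = a × b. By Fisher's transformation z = atanh(r) × √(90 − 3), and the rejection rate is Φ(z − 1.96) + Φ(−z − 1.96). Simulated rates use 6,000 trials per setting.

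| a, b | r | z | Formula | Simulated, no blood pressure | Simulated, blood pressure added |
|---|---|---|---|---|---|
| 0.2, 0.3 | 0.06 | 0.56 | 8.7% | 9.2% | 4.5% |
| 0.3, 0.3 | 0.09 | 0.84 | 13.4% | 14.1% | 5.3% |
| 0.3, 0.4 | 0.12 | 1.12 | 20.3% | 20.4% | 5.4% |
| 0.4, 0.4 | 0.16 | 1.51 | 32.5% | 32.9% | 5.1% |

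**Step 2: BMI change in the model.** This is closer to the planned multivariable step. Assume BMI change correlates 0.4 with EAT change and with blood pressure change only through EAT. The EAT coefficient keeps its bias and its standard error grows by 1/√(1 − 0.4²), so z is multiplied by 0.917. The extremes become 0.56 × 0.917 = 0.51 (8%) and 1.51 × 0.917 = 1.38 (28%). Simulation gives 8-27%, and about 4-6% once error-free blood pressure change is added.

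**Step 3: arm effects and wider assumptions.** Here the arm effect is 0.6 SD on EAT change and 0.5 SD on blood pressure change; BMI change correlates 0.3 with each; n = 90; 2,500 trials per setting. Entries are the rates at which EAT is significant.

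| Within-arm a, slope of LVM on blood pressure | EAT + BMI | + blood pressure | + arm only | + both |
|---|---|---|---|---|
| 0, 0.4 | 5.3% | 4.8% | 6.4% | 4.6% |
| 0.2, 0.3 | 7.4% | 5.2% | 6.5% | 5.2% |
| 0.2, 0.4 | 9.1% | 4.8% | 7.1% | 5.0% |
| 0.3, 0.5 | 22.0% | 4.9% | 18.1% | 4.5% |
| 0.4, 0.5 | 40.2% | 4.6% | 33.7% | 5.0% |

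The last two rows use a stronger blood pressure-LVM link than the range above. Adding arm without blood pressure removes little of the bias.

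**Step 4: why a shared treatment effect is not enough.** With equal arms, arm effects of 0.6 and 0.5 SD induce a covariance of 0.6 × 0.5 × 0.25 = 0.075. The overall SDs are √1.09 = 1.044 and √1.0625 = 1.031, so the induced correlation is 0.075/(1.044 × 1.031) = 0.07. Multiplied by b = 0.3-0.4, it gives r = 0.02-0.03 and a rejection rate of 5-6%.

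**Step 5: cuff error.** If measured blood pressure change had reliability 0.5 (assumed), adding it would leave 5-11% with BMI in the model and 5-14% without.

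The p < 0.1 screen was not applied in these rates. If BMI fails the screen, the model falls back to EAT alone, as in Step 1.

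**The case against.** **A reader might infer that the drug lowers EAT and blood pressure together and that this by itself creates the EAT-LVM association.** The documents do not support that. They mention osmotic diuresis only as a possible source of weight loss and never say that blood pressure falls. Step 4 also shows that a shared treatment effect leaves the error rate near 5%. The bias needs EAT and blood pressure changes to move together among patients in the same arm. That is plausible, since both may follow individual weight loss, but no section documents it.

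**BMI may already absorb the problem.** If the EAT-blood pressure link runs wholly through weight change, a model containing BMI change gives about 5% without blood pressure. This is a best case: BMI must survive the p < 0.1 screen, and a diuresis route would not be covered.

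**The comparison with BMI, waist and waist-hip ratio is a comparison of markers.** This is fair: independence from other fat measures is what that sentence is for. The weak point is the preceding selection step, which speaks of independent determinants. Its wording is loose enough for an analyst to add blood pressure, but it does not prespecify it, and the screen could drop it.

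**Adjustment has limits.** If EAT acts on the ventricle partly through blood pressure, adjusting removes part of a real effect, and cuff error leaves some bias behind. Both points stand. They are reasons to show both models, not to leave blood pressure out.

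**The causal claim has larger gaps.** No mediation analysis is planned and arm is missing from these models. This also stands: one covariate will not establish that LVM falls through EAT.

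**Conclusion.** The omission is real and worth correcting, but its reach is limited. As written, the plan can credit EAT with an effect that belongs to blood pressure, provided the two changes are correlated between patients within an arm.

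Under the assumed correlations (0.2-0.4 and 0.3-0.4, n = 90), the chance of falsely declaring EAT independent is about 8-27% with BMI change in the model and 9-33% with EAT alone. It is about 5% with error-free blood pressure change added, and somewhat higher with realistic cuff error. These figures illustrate size and are not estimates for this trial. With no within-arm correlation there is almost no inflation.

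The primary EAT endpoint and the randomised F versus M comparison of LVM are not affected. Only the independent-determinant and through-EAT conclusions are.

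**What to change.** In the Study Hypothesis 2 multivariable model for LVM change:

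1. Enter change in systolic blood pressure as a fixed term, exempt from the p < 0.1 screen, together with treatment arm.
2. Report the EAT coefficient with its confidence interval both with and without blood pressure change.
3. Call EAT independent only if its coefficient holds with blood pressure in the model. Otherwise describe the result as an association.
4. As a sensitivity analysis, add an indicator for a change in blood-pressure drugs, taken from the concomitant medication record. Do not exclude those patients: selecting on a post-randomisation event can introduce bias of its own.

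The cost is one or two degrees of freedom in the main model and no new visits or measurements. The EAT coefficient will be attenuated if EAT acts partly through blood pressure, which is why both versions are reported. Visit Procedures could also name blood pressure explicitly, to remove doubt that it is taken at all three visits.

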Echocardiographic epicardial fat is a marker of visceral fat. In fact, EAT strongly reflects the intra-abdominal visceral fat as measured by MRI and better than waist circumference does (9-11). In a multiple regression analysis that included waist circumference and epicardial fat thickness showed, intra-abdominal visceral fat was better and independently predicted by the epicardial fat that epicardial adipose tissue thickness ($r^2 = 0.44$, $p < 0.01$). Bland test confirmed the good agreement between the two methods. Other studies confirmed this finding in different populations. EAT is therefore an independent predictor of visceral adiposity and weakly reflects the obesity degree as measured by BMI. Subjects with higher waist circumference clearly show higher epicardial fat thickness, as previously reported. Ectopic fat deposition may occur within the organs and affect the function. EAT is associated with proton magnetic resonance spectroscopy ($^1\text{H-MRS}$) intra-myocardial fat (12). Hence, EAT can be considered primarily a simple and objective marker of visceral adiposity.

Echocardiographic epicardial fat predicts Cardiovascular Risk

An escalating number of evidences indicate that EAT measurement may play a role in the stratification and prediction of the cardio-metabolic risk (13-35). Several clinical studies showed that epicardial fat thickness is also related to traditional and novel cardiovascular risk factors. Epicardial fat thickness is significantly higher in subjects with metabolic syndrome than in those without. When cardio-metabolic parameters are considered separately, epicardial fat is independently associated with inflammatory markers and liver enzymes. EAT has been associated with the presence and severity of CAD in a large number of studies.

Epicardial Fat and LVM

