- a) Dapagliflozin causes a rapid and significant reduction of EAT in type 2 diabetic patients
- b) Dapagliflozin-induced EAT reduction would be associated with a significant reduction of LV mass, independent cardiovascular risk factor.

ENDPOINTS:

Primary Endpoint: EAT (Epicardial fat thickness) will be measured with echocardiography according to the method described and validated by [name] et al. Full description of the measurement is reported in the section "Methodology"

Secondary Endpoint: LVM (left Ventricular Mass) will be measured with echocardiography according to the standard formula, fully described in the section "Methodology"

SPECIFIC OBJECTIVES

Primary Objective:

- a) Does treatment with Dapagliflozin cause a significant decrease in EAT in subjects with type 2 diabetes?

Secondary Objective:

- b) Does treatment with Dapagliflozin cause a significant decrease in LVM, through the reduction of EAT, in subjects with type 2 diabetes?

[figure not shown]
STUDY DESIGN

This will be an interventional, double-blind, parallel group, placebo controlled study in 100 overweight/obese type 2 diabetic subjects who are taking Metformin as monotherapy.

Individuals will be randomized in two groups of 50 patients, to receive additional Farxiga (Dapagliflozin) (F-group) or to remain on Metformin (M-group) plus placebo orally once daily.

[figure not shown]
- F-group: Dapagliflozin will be administered at the starting dose of 5 mg once daily, then if no safety issues will occur, it will be titrated up to 10mg once daily after 2 weeks. Metformin (from 500 mg twice daily to a maximum of 1000 mg twice daily) regimen will be continued to achieve fasting glucose between 80 and 140 mg/dl.
- M-group will be treated with Metformin plus placebo orally once daily for the duration of the study. Metformin (from 500 mg twice daily to a maximum of 1000 mg twice daily) regimen will be continued to achieve fasting glucose between 80 and 140 mg/dl.

Both groups will receive lifestyle and diabetes education, as part of the standard care.

STUDY TIMETABLE

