We expect that Dapagliflozin will cause a significant decrease in EAT, but much smaller when compared to weight loss interventions such as a VLCD. EAT decrease has been shown to vary (between -12% and -32%) after different interventions. EAT reduction is anticipated to be between -15% and -25% after 3 months of treatment with Dapagliflozin. A hypothesis of at least 15% reduction in EAT is based on: a) the previously reported weight-loss caused by Dapagliflozin, b) previously-reported responsiveness (decrease) of EAT to pharmacological agents targeting the fat. A reduction of 15%, an absolute difference of 1.2 mm from baseline, will be considered not only statistically, but clinically significant of visceral fat reduction. It is worthwhile to note that a reduction of 0.4 and 1.4 mm in EAT after atorvastatin and bariatric surgery, respectively, was previously considered statistically and clinically significant. However, it is possible to expect a larger difference after 6 months of treatment

Given the reference value and the expected difference in EAT, the statistical power of the study (two-sided, $\alpha=0.05$) was calculated.

Outcome	Reference value \pm SD	Expected Difference	Detectable difference with 80% power $\alpha=0.05$	Detectable difference with >99% power $\alpha=0.05$
EAT (mm)	8 ± 3	-15-or -25%	-15% (absolute difference = 1.2)	-25% (absolute difference = 2)

A convenience sample of 50 individuals for each group will therefore provide the statistical power (80%) to detect an expected difference of -15% in the EAT before and after treatment with Dapagliflozin. Baseline SD of 3 is expected to lower to approximately 2 for the expected change. The expected change of SD will assure significant statistical power of the comparative test.

Study Hypothesis 1 Dapagliflozin causes a significant and rapid decrease in EAT. Comparative statistical analysis between F and M-group will be performed to tests this hypothesis. Continuous variables will be considered as age-adjusted and sex-adjusted means with their standard deviations (SDs). Two-tailed $p < 0.05$ indicates statistical significance. ANOVA model with adjustment for baseline will be used to calculate the changes (Δ) in EAT between baseline, 3 and 6 months in both F and M-group.

Study Hypothesis 2

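### EAT is to be compared with BMI, waist and waist-hip ratio as a predictor of change in LVM, but no test, interval or rule for a difference between predictors is specified (minor)

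*Combined protocol and SAP*

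**What the plan says.** All of the relevant text is in STATISTICAL CONSIDERATIONS of the combined protocol and SAP, mostly under Study Hypothesis 2.

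- The aim: "Echocardiographic epicardial fat will be compared to BMI, waist circumference and to waist-hip ratio as independent predictor of Δ LVM".
- The univariate step: "Relations between Δ epicardial fat, Δ BMI, Δ waist circumference and Δ LVM will be calculated using simple linear regression analysis". Waist-hip ratio is part of the comparison but is not in this list.
- The multivariable step: "Variables with a $p < 0.1$ value on univariate analysis will be entered in different multivariate analysis models to assess the independent determinants".
- The ROC step: "The optimum sensitivity and specificity of threshold values of EAT to predict reduction in LVM will be examined by receiver operating characteristics (ROC) analysis". No curve is planned for BMI, waist or waist-hip ratio.
- The significance level, given under Study Hypothesis 1: "Two-tailed $p < 0.05$ indicates statistical significance".

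The plan does not name the quantity on which the predictors are to be compared. It gives no test or confidence interval for a difference between them, and no rule for calling one better.

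**The concern.** A comparison of predictors asks whether one carries more information about ΔLVM than another. Its null hypothesis is that the two are equal. A coefficient test has a different null: that this predictor adds nothing once the others are in the model. One coefficient can pass p < 0.05 and another miss it when the two predictors are equally strong.

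Because the plan offers only coefficient tests, the natural way to report the announced comparison is by which predictor stayed significant. The background section on echocardiographic EAT as a marker of visceral fat argues in a similar way. It cites a multiple regression that held both waist circumference and EAT, and takes from it that EAT was the better predictor of intra-abdominal fat as well as an independent one.

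What is at stake is a published statement that EAT predicts change in LVM better than simple anthropometry, or the opposite statement, resting on an analysis that cannot distinguish the two.

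**Working it through.** **Plan's own figure.** There is none for this comparison. The stated 80% power concerns the primary EAT endpoint and does not enter here.

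**Inputs from the documents.** Two-sided 0.05. STUDY DESIGN: "Individuals will be randomized in two groups of 50 patients", so 100 in total. COMPLIANCE AND RETENTION STRATEGY expects attrition below 10%, so at worst 100 × 0.9 = 90 completers.

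**Assumed inputs.** The documents give no correlations between change scores. I take each predictor to have the same true correlation r = 0.2, 0.3 or 0.4 with ΔLVM, and a correlation ρ = 0.3 to 0.6 between EAT and one rival. By construction neither predictor is better.

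**Step 1: one case by hand (r = 0.3, ρ = 0.3, n = 90).** With both predictors in one model:

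- Standardised coefficient of each: r/(1+ρ) = 0.3/1.3 = 0.231.
- R² = 2r²/(1+ρ) = 0.18/1.3 = 0.138.
- SE = √[(1−R²)/((n−3)(1−ρ²))] = √[0.862/(87 × 0.91)] = 0.104.
- Expected t = 0.231/0.104, about 2.21 from unrounded values, against a critical value of 1.99.
- Chance that a given predictor is significant ≈ Φ(2.21 − 1.99) = Φ(0.22) ≈ 0.59.
- Chance that EAT is significant and the rival not, if the two estimates were independent: 0.59 × 0.41 = 0.24. The estimates are negatively correlated (−ρ), which raises this to about 0.29.

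**Step 2: simulation of the pairwise model.** Multivariate normal changes, n = 90, 20,000 replicates per cell, no univariate screen. The direct test is Williams' test for two dependent correlations.

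| ρ | r | EAT significant, rival not | Rival significant, EAT not | Direct test wrongly favours EAT |
|---|---|---|---|---|
| 0.3 | 0.2 | 23.5% | 23.7% | 2.7% |
| 0.3 | 0.3 | 27.9% | 28.2% | 2.4% |
| 0.3 | 0.4 | 12.4% | 11.8% | 2.4% |
| 0.6 | 0.2 | 15.0% | 15.2% | 2.4% |
| 0.6 | 0.3 | 27.5% | 27.9% | 2.4% |
| 0.6 | 0.4 | 34.5% | 33.1% | 2.4% |

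With the p < 0.1 screen applied first, the EAT-only rates are 26%, 29% and 12% at ρ = 0.3, and 19%, 31% and 34% at ρ = 0.6. The screen is therefore not the cause.

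**Step 3: sensitivity.** The plan does not say whether the arms are pooled. With 50 patients (one arm), r = 0.2 to 0.4 and ρ = 0.3 to 0.7, the EAT-only rate is 10% to 31%. The problem shrinks when both predictors are strong and overlap little: at n = 90 and r = 0.5 it is 0.9% for ρ = 0.3 and 10% for ρ = 0.5, but still 32% for ρ = 0.7.

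**Step 4: BMI and waist in the same model as EAT** (n = 90, no screen; the three figures are for r = 0.2, 0.3 and 0.4).

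| EAT–rival correlation | BMI–waist correlation | EAT only | A rival but not EAT |
|---|---|---|---|
| 0.3 | 0.8 | 23.3 / 43.5 / 53.1% | 11.7 / 11.6 / 7.2% |
| 0.6 | 0.8 | 11.7 / 22.1 / 34.4% | 11.8 / 16.2 / 19.8% |
| 0.7 | 0.8 | 8.4 / 15.1 / 23.4% | 11.5 / 16.4 / 23.1% |
| 0.6 | 0.6 | 9.0 / 14.4 / 19.8% | 17.9 / 30.3 / 43.8% |

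The error leans towards EAT in the first row, is about even in the third and leans against EAT in the fourth.

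**Step 5: what a direct comparison could show.** At r = 0.3, ρ = 0.3 and n = 90, each predictor alone has true R² = 0.3² = 0.09. The observed difference in R² between the two has a simulated 95% range of about −0.14 to +0.14.

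**The case against.** The strongest reply is that the plan never says EAT will be declared better because it is significant and a rival is not. The comparison sentence follows one stating that variables "will be entered in different multivariate analysis models to assess the independent determinants of Δ LVM, as dependent variables". It can be read as asking only whether ΔEAT remains associated with ΔLVM after adjustment for anthropometry. For that question a coefficient test is the right tool. This stands in part: the decision rule is inferred, and the multivariable model is a sound description of independent association. It does not remove the gap, because the plan also announces a comparison and gives no other way to make it.

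A reader might go further and infer that the procedure is tilted towards EAT. BMI, waist and waist-hip ratio overlap and would weaken one another in a joint model, and the background says "EAT is therefore an independent predictor of visceral adiposity and weakly reflects the obesity degree as measured by BMI". The documents do not support this. That sentence concerns levels, not changes, and BMI only; the same section says that EAT is clearly higher where waist circumference is higher. The plan speaks of different multivariate models, which may be pairwise, and there the error is symmetric. In a joint model the direction depends on correlations that the documents do not give (step 4).

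Nor does the point undermine the case in SIGNIFICANCE AND INNOVATION. That case is about EAT as a marker of visceral fat, not about predicting LVM.

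**Conclusion.** The concern holds as a gap in specification. A comparison between predictors is announced, and nothing in the plan can carry it out validly. If it is read from significance in a two-predictor model, equally good predictors give an EAT-only result in about 12% to 35% of trials and a rival-only result about as often. A direct test errs in EAT's favour in 2% to 3%.

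These rates rest on 90 completers, r of 0.2 to 0.4 and ρ of 0.3 to 0.6, all but the first assumed; outside that range they can be much smaller. The higher figures in step 4, up to 53%, need one particular correlation pattern and should not be quoted as the size of the problem.

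The point is minor. It touches one secondary, explanatory analysis and leaves the primary EAT comparison and the between-group LVM comparison as they are.

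**What to change.** Keep the multivariable model and describe it as an estimate of EAT's independent association with ΔLVM. Replace the comparison sentence with wording such as:

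*The strength of ΔEAT as a predictor of ΔLVM will be compared with that of ΔBMI, Δwaist circumference and Δwaist-hip ratio, one at a time and in the same patients, by the difference in R² (or in standardised coefficients) with a bootstrap 95% confidence interval. One measure will be called a better predictor only if the interval excludes zero. Significance of one predictor and non-significance of another will not be taken as evidence of a difference.*

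The cost is one paragraph and a short computation on data already being collected, with no extra patients, visits or measurements. The downside is precision: with about 90 patients the interval will be wide relative to the R² values likely to be seen (step 5), so a claim that either measure is better will be hard to establish.
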